11.3.2.3 Severity

The severity of all AEs must be evaluated by the PI or, if the PI does not have a medical background, by a medically qualified individual (MD/DO). The severity classifications are:

- **Severe** – Extreme distress, causing significant impairment of functioning or incapacitation; interferes significantly with subject's usual function; prevents normal everyday activities.
- **Moderate** – Sufficient discomfort is present to cause interference to some extent with subject's usual function or normal everyday activity.
- **Mild** – Awareness of symptoms that are easily tolerated, causing minimal discomfort and not interfering with subject's usual function or normal everyday activities.

Note the distinction between the severity and the seriousness of an AE. A severe event is not necessarily a serious event. For example, a headache may be severe (interferes significantly with subject's usual function) but would not be classified as serious unless it met one of the criteria for SAEs, listed above.

11.3.2.4 Causality Assessment

An AE (serious or non-serious) is considered “study-related” if the causality assessment is possible, probable, or very likely. The PI or, if the PI does not have a medical background, a medically qualified individual (MD/DO) determines the causality by using the following definitions:

- **Not related** – an AE that is not related to the participation in the study.
- **Doubtful** – an AE for which an alternate explanation is more likely (e.g. concomitant drug), or the relationship in time suggests that a causal relationship is unlikely.
- **Possible** – an AE that might be a result of participation in the study. An alternative explanation is inconclusive and the relationship in time is reasonable so a causal relationship cannot be excluded.
- **Probable** – an AE that might be a result of participation in the study. The relationship in time is suggestive (e.g. confirmed by the challenge). An alternative explanation is less likely.
- **Very Likely** – an AE that is listed as a possible adverse reaction and cannot be reasonably explained by an alternative explanation. The relationship in time is very suggestive (e.g. confirmed by dechallenge and rechallenge).

11.3.3 Procedures for Reporting Adverse Events

All AEs will be reported from the time a signed and dated ICD is obtained until completion of the subject’s last study procedure or visit (or termination if the subject terminates early from the study for any reason).

AEs that occur between end of study and 30 calendar days after completion of the study will only be reported to the Sponsor if they are serious. SAEs are reportable beyond this period if the event is considered study-related. The Sponsor will evaluate any safety information that is spontaneously reported by the PI beyond the time frame specified in the protocol.

Subjects are encouraged to report AEs spontaneously and in response to questioning during the visit (e.g. if they have had any side effects/issues or changes in their health). For each AE reported by the subject or observed by the study team, the study team member should notify the PI, Study Physician, or designee, who will collect information about the event.

All AEs, regardless of seriousness, severity, or presumed relationship to study procedures, must be recorded using medical terminology on the Sponsor provided AE form and then entered into the Electronic Data Capture (EDC), Medidata Rave AE Universal Database. These events must then be entered into the Medidata Rave AE Universal Database within 5 business days of the site’s awareness. The DPR review of AEs/SAEs in Medidata Rave AE Universal Database will be conducted within 5 business days of each entry into Medidata Rave AE Universal Database in order to escalate any potential safety signal to the Department Head.

Whenever possible, diagnoses should be given when signs and symptoms are due to a common etiology (e.g., cough, runny nose, sneezing, sore throat, and head congestion should be reported as “upper respiratory infection”). The PI or, if the PI does not have a medical background, a medically qualified individual (MD/DO) designee, must record or confirm their opinion concerning the

seriousness, severity, and relationship of the AE to the study. All measures required for AE management must be recorded and reported according to Sponsor instructions.

The PI or designee must also report AEs to the appropriate IRB unless otherwise required and documented by the IRB.

If a **SAE** occurs, in addition to the above reporting procedures, the Site will **immediately** notify the Study Manager and Study Director by telephone or encrypted e-mail (see Appendix III for Contact Information)

Subsequent to a telephone or encrypted e-mail report of an SAE, a Clinical Trial SAE Report Form (provided to the study site at the initiation of the study) must be completed by the investigational staff with as much information as possible (however at a minimum, the subject identification number, name of investigational product [if applicable], SAE description, investigator's assessment of causality, and name of site personnel reporting event are required), signed by the PI (or the medically qualified designee), and securely transmitted to the Study Manager and Study Director **within 24 hours** of becoming aware of the event.

This timeframe also applies to additional new information (follow-up) on previously forwarded SAE reports.

In the rare event that the Investigator's site does not become aware of the occurrence of a SAE immediately (e.g., if an outpatient study subject initially seeks treatment elsewhere), the Investigator's site is to report the event immediately after learning of it as described and document the time of the study site's first awareness of the SAE.

The Study Manager or designee will notify the DPR within 1 calendar day of SAE information receipt. The DPR will request more information as necessary. The Study Manager or designee will send an e-mail appropriate document to Sponsor's OCMS group per local procedures within the following timelines:

- fatal/life-threatening reports: within 2 calendar days from regulatory clock start date
- other SAEs and pregnancy exposure reports: within 3 calendar days from regulatory clock start date

For all SAEs, the PI is obligated to pursue and provide information to the Sponsor in accordance with the timeframes for reporting specified above. In addition, the PI may be requested by the Sponsor to obtain specific additional follow-up information in an expedited fashion. This information may be more detailed than that captured on the AE Form. In general, this will include a description of the SAE in sufficient detail to allow for a complete medical assessment of the case and independent determination of possible causality. Information on other possible causes of the event, such as concomitant medications and illnesses, must be provided.

In the case of a subject death, a summary of available autopsy findings (if available) and death certificate should be collected if permission is obtained from the subject's family.

For a hospitalization, a copy of the hospital discharge summary should be requested. If obtained, these documents (with subject's personal identifiers redacted) should be securely submitted as soon as possible to the Sponsor or its designated representative.

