6.2.2 Exclusion Criteria

Subjects with any of the hereafter criteria must be excluded from the study:

- I. Individuals with known allergies or sensitivities to common topical skincare products, including adhesives and/or cyanoacrylate (super glue) or ingredients to the test materials for a specific test panel.
- II. Deprived from liberty by a judiciary or administrative decision.
- III. Having undergone organ excision (kidney, lung, spleen, and liver), an organ transplant, or a skull concussion with extended loss of consciousness within the last 5 years or with present symptoms and/or side effects.
- IV. Individuals with self-reported UNCONTROLLED metabolic conditions, such as diabetes, hypertension, hyper/hypothyroidism, hypercholesterolemia, etc.
- V. Individuals with CONTROLLED health conditions may be excluded from the study at the discretion of the PI or designee:
 - Subjects with conditions that do not affect the skin, such as hypertension and hypercholesterolemia, could be enrolled when their health condition is managed through diet, medication, etc.
 - Subjects with conditions, which might affect the skin, such as hyper/hypothyroidism, diabetes must be excluded, regardless whether their health condition is controlled or not.
- VI. Subjects who are taking medication for chronic conditions (e.g., insulin, antihistamines, steroidal and non-steroidal anti-inflammatory drugs, antibiotics, etc...) – exception could be made for hypercholesterolemia as per point IV.
- VII. Individuals with adult asthma and/or epilepsy.
- VIII. Skin diseases on tested sites (e.g., psoriasis, eczema, erythema, edema, scars, wounds, melanomas, etc.), which may influence the outcome of the study;
 - a. Supplemental Consent
During the eligibility screening, individuals who indicate that they have previously had eczema will be advised of the Koebner phenomenon, which refers to the appearance of these conditions either at the patch site or unrelated sites. If the individual chooses to participate in the study, 2 copies of a supplemental consent form will be signed by the subject (1 for the study files and 1 will be given to the subject).
- IX. Subjects who are self-reported to be pregnant, lactating or planning to become pregnant; females of child-bearing potential who are unwilling or unable to use an acceptable method of contraception during the study.
- X. Male subjects who have a pregnant partner.

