1. The PI or designee will interview the subjects to collect and record any AEs or changes to health/concomitant medications that may have occurred since the previous visit. Subjects will also be interviewed for compliance with study directions. Refer to Adverse Event Reporting section.
2. Patches applied during the prior visit will be removed by clinic personnel.
3. Each test site will be evaluated for irritation/reactions by the delegated evaluator.
4. Test sites may be re-delineated as needed, as described in Visit 1.

5. New test material dosed patches and an undosed negative control patch will be applied to the same test sites as described for Visit 1.

Make-up Visit

As necessary, a subject may complete a make-up patching visit. Make-up will be conducted 48-72 hours post Visit 12. Subject will return to site for Visit 13 for the collection of Follicular Biopsies. Subjects will report to the site at their scheduled visit time and will participate in the following procedures:

1. The PI or designee will interview the subjects to collect and record any AEs or changes to health/concomitant medications that may have occurred since the previous visit. Subjects will also be interviewed for compliance with study directions. Refer to Adverse Event Reporting section.
2. Patches applied during the prior visit will be removed by clinic personnel.
3. Each test site will be evaluated for irritation/reactions by the delegated evaluator.
4. Test sites may be re-delineated as needed, as described in Visit 1.
5. New test material dosed patches and an undosed negative control patch will be applied to the same test sites as described for Visit 1.

Visit 13:

Visit 13 will be conducted 48-72 hours post Visit 12. Subjects will report to the site at their scheduled visit time and will participate in the following procedures

1. The PI or designee will interview the subjects to collect and record any AEs or changes to health/concomitant medications that may have occurred since the previous visit. Subjects will also be interviewed for compliance with study directions. Refer to Adverse Event Reporting section.
2. Patches applied during the prior visit will be removed by clinic personnel.
3. Each test site will be evaluated for irritation/reactions by the delegated evaluator.
4. A delegated clinician will collect follicular biopsies from each test site as described below in the *Study Instrument(s)* section.

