5. The PI or designee will interview the subjects to collect and assess any AEs or changes to health.
6. After all assessments are completed, subjects will leave site.

Note: 72-hour exposure time is only applicable for visits conducted on Friday and/or to allow for site closed days.

Site Irritation / Reaction Grading

At visits 2 through 13 (and makeup visit if applicable), the designated test sites will be graded for irritation/reactions using the North American Contact Dermatitis Group (NACDG) grading scale. Sites will be adequately illuminated using lighting provided by a 60-watt incandescent blue day light bulb.

NACDG Grading Scale

- 0 No reaction
- +0.5 Macular erythema
- +1 Indurated erythema
- +2 Erythema, infiltration and vesicles
- +3 Bullous reaction or ulcer

If irritation develops as indicated by the NACDG score, the patch type may be changed or patch applications may be skipped for specific sites. Skipping a patch application should be documented as a protocol deviation. This may also have an impact on the follicular biopsy process at the final study visit. Any changes made to the patch type, application schedule, or biopsy procedures will be documented in the appropriate source documents.

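### Non-serious reactions to the follicular biopsy or the last patch that first appear after Visit 13 need not be reported to the Sponsor, and no later contact is scheduled

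*Combined protocol and SAP*

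**What the plan says.** Section 11.3.3 sets two reporting periods. The first opens at signed consent, covers every AE, and closes with the "last study procedure or visit (or termination if the subject terminates early from the study for any reason"). In the second, AEs arising "between end of study and 30 calendar days after completion of the study will only be reported to the Sponsor if they are serious". Two further sentences extend this: "SAEs are reportable beyond this period if the event is considered study-related", and "The Sponsor will evaluate any safety information that is spontaneously reported by the PI beyond the time frame specified in the protocol".

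Section 9.1 gives Visit 13 six steps: an interview on AEs and compliance, patch removal, irritation grading, the biopsy ("A delegated clinician will collect follicular biopsies from each test site as described below"), a second interview on AEs, and departure ("After all assessments are completed, subjects will leave site"). Neither the activity table in Section 4 nor Section 5 has any visit, call or skin reading after Visit 13.

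Section 11.3.2.1 counts signs or symptoms resulting from a study procedure as AEs. It also says that mild erythema, edema, dryness, itching, burning and similar signs are clinical endpoints and not AEs, whereas persistent moderate-to-severe symptoms, or reactions with elevation such as papules or vesicles, are AEs. Exclusion criterion I in Section 6.2.2 bars people with known sensitivity to skincare products, "including adhesives and/or cyanoacrylate (super glue").

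**The concern.** The reporting period for non-serious AEs closes at the same visit at which the biopsy is taken and the last patch comes off. The biopsy presses glue on a slide against each site and pulls it away, on skin that has been patched for four weeks. The protocol treats glue and adhesive sensitivity as a hazard, but the exclusion can only screen out sensitivities already known.

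At stake is the completeness of the AE summary that Section 11.3.2.1 promises for everyone who signed consent. A vesicular reaction noticed before the subject leaves is an AE; the same reaction noticed the next day is one that nobody is obliged to report to the Sponsor. Section 11.3.2.3 states that a severe event is not necessarily a serious one, so even a severe site reaction could fall in the gap. The comedogenicity result itself is not affected.

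**Working it through.** There is no stated figure to reproduce. The check sets the order of Visit 13 against the reporting rules.

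1. **Position of the biopsy and last patch.** Section 9.1 puts patch removal at step 2, grading at step 3, the biopsy at step 4, the second AE interview at step 5 and departure at step 6. Section 5 places Visit 13 after any make-up visit, so it is the last visit either way.
2. **Reaction evident before departure.** It can be picked up at step 5, inside the all-AE period of Section 11.3.3. If study-related, it is followed under Section 11.3.4.1 to resolution, a stable endpoint or at least 30 days after completion. Captured.
3. **Serious reaction starting after departure.** Reportable for 30 calendar days, and beyond that if study-related (Section 11.3.3). Captured, provided the site hears of it.
4. **Non-serious reaction starting after departure.** The serious-only rule applies, so there is no duty to report it to the Sponsor. Scheduled observation after Visit 13 is 0 days. Not captured.
5. **Does another rule close case 4?** Section 11.3.4.1 governs follow-up of study-related AEs; it does not lengthen the period in which new ones are reported. The sentence on information volunteered by the PI commits the Sponsor to evaluate what it receives but places no duty on the site to send it.
6. **Which events in case 4 are AEs at all?** Only those that meet Section 11.3.2.1. Mild expected signs are not AEs at any time.
7. **Number of sites.** Section 9.1 allows up to 6 test sites per subject and Section 7 up to 18 subjects: 6 x 18 = 108 biopsied sites per panel. With the 15 completers that Section 7 aims to ensure: 6 x 15 = 90. Both assume all six sites are used and biopsied. The product chart in Appendix I is blank, and Section 9.2 allows the biopsy to be omitted at sites graded 2 or more. These are counts of sites, not of events. No reaction rate is given, so no number of missed events follows.

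**The case against.** A reader might infer that the biopsy is the final act of the study with no AE question after it, so that biopsy reactions as a class escape collection. The documents do not support that: step 5 is a second AE interview placed after the biopsy, and serious reactions stay reportable.

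A reader might also infer that a subject's telephone call would be disregarded. That goes too far. The restriction concerns what is reported to the Sponsor. Section 11.3.3 encourages subjects to report spontaneously, has the study team collect information on each reported event, and leaves the PI free to pass on late information. A route exists; what is missing is the obligation. The instructions handed out at Visit 1 are not reproduced in the protocol, so they may already ask subjects to call, and this cannot be judged.

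It is tempting to add that each earlier application is re-examined 48-72 hours after removal and the last one is not. The comparison is not like for like. A new patch goes on the same site at each interim visit, so the next grading reflects both applications, and the last application is itself graded at removal.

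Finally, many site reactions would be mild and so would not be AEs under Section 11.3.2.1 even inside the reporting period. That shrinks the gap but does not remove it, because persistent moderate-to-severe or elevated reactions do count. What stands after these points is case 4 of the check.

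**Conclusion.** The concern holds in a narrow form. Non-serious AEs caused by the biopsy or the last patch, with onset after the subject leaves Visit 13, are outside mandatory reporting under Section 11.3.3, and no scheduled contact would find them. Immediate reactions, serious reactions and the follow-up of study-related AEs already identified are covered.

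The size is unknown. The ceiling of 108 biopsied sites per panel describes exposure only. A reader might infer that the AE summary is bound to understate site reactions; the documents show only that it could, since they give neither a reaction rate nor a time to onset. The conclusion rests on reading the end of study, for each subject, as completion of Visit 13, and on the consent and instruction sheets, which were not available, adding no reporting duty. It is a cheap improvement to safety capture and does not bear on the validity of the primary comparison.

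**What to change.** In Section 11.3.3, amend the 30-day rule so that AEs in that period are reported to the Sponsor if they are serious or are assessed as study-related, meaning possible, probable or very likely in the categories of Section 11.3.2.4. State that this includes test-site reactions meeting the AE definition in Section 11.3.2.1, and that mild expected signs remain excluded as now.

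In the Visit 13 steps of Section 9.1, add that subjects are asked to call the site about any reaction at a patch or biopsy site during that period. Follow the resulting events under Section 11.3.4.1.

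The cost is one amended sentence, one added instruction and a few more non-serious AE entries, with no extra visit or procedure. The change creates a duty to report but no active observation: capture would still depend on subjects calling. If the sponsor and investigator want active detection, a scheduled safety contact after Visit 13 would be needed, with its timing for them to decide.

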11.3.4 Monitoring and Resolution of Adverse Events

11.3.4.1 Non-Serious AEs

All study-related AEs will be followed until resolution, until a stable clinical endpoint is reached, or at least 30 days post-study withdrawal/completion. This information will be captured in the source document and entered into Medidata Rave AE Universal Database.

11.3.4.2 Serious AEs (SAEs)

The PI or, if the PI does not have a medical background, the medically qualified designee (MD/DO) will monitor SAEs until resolution or until one of the conditions in 11.3.4.3 is met. The information will be captured in the source document and entered into Medidata Rave AE Universal Database. The PI/designee will also document follow-up information on an updated Clinical Trial SAE form, which will be reviewed by the PI or medically qualified individual designee and sent securely to the Study Manager or designee. The Study Manager or designee will forward the document(s) to the DPR and Study Director or designee, and to OCMS per local procedures.

11.3.4.3 Resolution

The PI will be required to assess the outcome of each AE as one of the following:

- Resolved;
- Not Resolved;
- Fatal;
- Resolved with sequelae;
- Resolving;
- Unknown.

Serious AEs that have not been resolved by the end of the study, or that have not been resolved upon discontinuation of the subject's participation in the study, must be followed until any of the following occurs:

- the event resolves
- the event stabilizes
- the event returns to baseline, if a baseline value is available
- the event can be attributed to factors unrelated to study conduct
- when it becomes unlikely that any additional information can be obtained (subject or healthcare practitioner refusal to provide additional information, lost to follow-up after demonstration of due diligence with follow-up efforts).

11.3.5 Exposure In Utero

For investigational products within clinical studies, an exposure *in utero* (EIU) occurs if:

- A woman is exposed to the investigational product at any time between her last menses prior to conception through the delivery of the baby.

If any study subject becomes or is found to be pregnant during the study subject's participation, the PI must report the pregnancy to the Sponsor on a Pregnancy Notification Form (to be provided by the Sponsor when applicable). Initial notification via telephone to the Sponsor's study team contact must occur immediately upon the Investigator site's awareness of the pregnancy. The Pregnancy Notification Form must then be sent to the Sponsor within 24 hours of the site's awareness. The

information submitted should include the anticipated date of delivery (see below for information to document termination of pregnancy).

Follow-up is conducted to obtain pregnancy outcome information on all EIU reports. The PI will follow the pregnancy until completion or until pregnancy termination (i.e., induced abortion) and then notify the Sponsor of the outcome. The PI will provide this information as a follow-up to the initial Drug Exposure During Pregnancy Collection Form A and/or End of Pregnancy Collection Form B (provided by the Sponsor when applicable). The reason(s) for an induced abortion should be specified. An EIU report is not created when an ectopic pregnancy report is received since this pregnancy is not usually viable. Rather, a SAE case is created with the event of ectopic pregnancy.

The PI should follow the procedures for reporting SAEs if the outcome of the pregnancy meets the criteria for immediate classification as a SAE (i.e., spontaneous abortion, stillbirth, neonatal death, or congenital anomaly [including that in an aborted fetus, stillbirth, or neonatal death]). In the case of a live birth, the “normality” of the newborn can be assessed at the time of birth (i.e., no minimum follow-up period of a presumably normal infant is required before an End of Pregnancy Collection Form B can be completed). The “normality” of an aborted fetus can be assessed by gross visual inspection, unless pre-abortion test findings are suggestive of a congenital anomaly.

Additional pregnancy outcomes that are classified as SAEs and should be reported as such include:

- “Spontaneous abortion” includes miscarriage and missed abortion;
- All neonatal deaths that occur within 1 month of birth, without regard to causality;
- Any infant death after 1 month that the PI assesses as possibly related to in utero exposure to the investigational product.

